6.4. Treatment Compliance

Summaries of study treatment exposure and dose modifications (e.g., number of dose reductions, number of dose interruptions) will further characterize compliance. These analyses are described in Section 6.5 'Extent of Exposure'.

6.5. Extent of Exposure

Extent of exposure to GSK2857916 will be summarized.

The number of cycles administered to study treatment will be summarised with mean, median, standard deviation, minimum, and maximum. The number and percentage of subjects who received a given number of cycles (<4, 4, and >4 cycles) will be reported.

Dose intensity (dose delivered per cycle) will be summarized using mean, median, standard deviation, minimum, and maximum by cycle and overall. Dose intensity is the cumulative actual dose divided by the total number of cycles across the entire treatment period. A by subject summary listing of data on exposure to all study treatments will be produced.

Dose reductions will be summarised by number of reductions and reasons for reductions. Dose delays will be summarised by number of delays, reasons for the delays, and delay duration (days). The number and percentage of the delays 1-21, 22-42 and >42 days will be computed. Primary reasons for dose reductions and dose delays will also be summarized by cycle.

Duration of delays is defined as period from the expected start date of dose to actual start date of current dose. Calculation: (actual start date of current dose - expected start date of dose). Expected start date of dose = actual start date of previous dose + 21.

The summaries of dose modifications will be provided only if the data warrant.

All the dose reductions, dose escalations, infusion interruptions, incomplete infusions and dose delays will be listed separately.

A plot showing the number and percentage of subjects treated at different dose levels over time will be provided.

The duration of exposure to study treatment in days (from first day to last day of treatment) will be calculated. A horizontal bar graph of duration of treatment will be produced that displays duration of treatment in days for each subject.

6.6. Concomitant Medications

Concomitant medications will be coded using GSK Drug coding dictionary, summarized, and listed. The summary of concomitant medications will show the number and percentage of subjects taking concomitant medications by Ingredient. Multi-ingredient products will be summarized by their separate ingredients rather than as a combination of ingredients. Anatomical Therapeutic Chemical (ATC) classification Level 1 (Body System) information will be included in the dataset created but will not appear on the listing or summary.

Prophylactic Medication for Infusion-Related Reactions will be summarized by drug class and drug name and listed separately. Eye medications will be listed.

In the summary of concomitant medications, each subject is counted once within each unique ingredient. For example, if a subject takes Amoxicillin on two separate occasions, the subject is counted only once under the ingredient "Amoxicillin". In the summary of concomitant medications, the ingredients will be summarized by the base only, using CMBASECD and CMBASE. Note: In order to be considered a concomitant medication, the concomitant medication must have been taken at some point during the on-therapy window.

Blood products or blood supportive care products with onset date within the on-therapy window will be included in the summary tables. The frequency and percentage of subjects using blood products and blood supportive care products after the start of study medication will be provided. Supporting listings will also be provided.

6.7. Subsequent Anti-Cancer Therapies

The number and percentage of subjects that received chemotherapy, immunotherapy, hormonal therapy, biologic therapy, radioactive therapy, small molecule targeted therapy, as post study treatment anti-cancer therapy will be summarized. Time from study treatment discontinuation to the first post study treatment anti-cancer therapy will also be included in this summary table.

Follow-up anti-cancer therapy will be coded using GSK Drug coding dictionary, then summarized by ingredient. A listing of the type of follow-up anti-cancer therapy received (chemotherapy, immunotherapy, hormonal therapy, biologic therapy, radioactive therapy, and small molecule targeted therapy for each subject will be provided).

7. EFFICACY ANALYSES

7.1. Primary Efficacy Analyses

No primary efficacy analyses were planned.

7.2. Secondary Efficacy Analyses

Details of the planned displays are provided in [Appendix 12](#): List of Data Displays and will be based on GSK data standards and statistical principles.

Unless otherwise specified, endpoints / variables defined in Section [7.2.1.1](#) and Section [7.2.2.1](#) will be summarised using descriptive statistics, graphically presented (where appropriate) and listed.

7.2.1. Multiple Myeloma

7.2.1.1. Endpoint / Variables

7.2.1.1.1. Overall Response Rate

Overall Response Rate (ORR), is defined as the percentage of responders (subjects with confirmed stringent complete response (sCR), complete response (CR), very good partial response (VGPR), and partial response (PR) as assessed according to 2011 International Myeloma Working Group (IMWG) criteria (Appendix 1 in the protocol)). Only the assessments from the start of treatment up to the earlier of disease progression or the start of new anti-cancer therapy will be considered. Only new systemic anti-cancer drugs taken are considered as anti-cancer therapy (radiotherapy and surgeries are not considered as systemic anti-cancer therapy for the purpose of this analysis). .

Subjects with only one assessment (therefore not confirmed), or assessments of Not Evaluable or missing response will be treated as non-responders; i.e. they will be included in the denominator when calculating the percentage.

7.2.1.1.2. Response Confirmation Algorithm

The definitions and details to derive unconfirmed and confirmed response are outlined below. For both confirmed and unconfirmed response derivations, only responses assessments from the start of treatment up to the earlier of disease progression or the start of new anti-cancer therapy will be considered. Date associated with response was defined in Section [16.5.5](#)

Definitions:

1. The hierarchy of response classifications from high to low is as following: sCR, CR, VGPR, PR, MR, SD, PD and NE. Response was assessed according to the 2011 Uniform Criteria Consensus recommendations of the International Myeloma Working Group (See Appendix 1 of protocol).

2. Definition of two consecutive assessments: the two consecutive assessments should be taken from two different samples, and NOT based upon the splitting of a single sample.
 - a. No minimum time separation between two consecutive assessments is required to confirm response.
 - b. If there are two assessments separated by not evaluable (NE) or Missing assessment(s), collapse data by ignoring NE or Missing assessments.
 - c. If two consecutive assessments are on different dates, it is assumed that the two assessments are from different samples
 - d. If there are multiple assessments on the same date and there is no data to show that they are from different samples, it is assumed these assessments are from the same sample. Then only the response with the lowest magnitude will be selected as the response for that date.

Two-step algorithm for determining the best confirmed response

Step1. Determine the confirmed response sequentially at each time of disease assessment.

- A. For confirmed sCR, CR, VGPR, PR, MR, SD, two consecutive assessments are required.
 - a. For any two consecutive assessments with different magnitudes, the confirmed response is the response of lower magnitude.
 - b. For any two consecutive assessments with the same magnitude, the confirmed response is the response of that magnitude.
 - c. Although the response will be confirmed at the time of the second one of the two consecutive assessments, the date of the first one of the two consecutive assessments will be the date of this confirmed response.

Table 4 Summary of the criteria for confirmation of sCR, CR, VGPR, PR, MR, SD

Response at one time-point of two consecutive assessments	Response at the other time-point of two consecutive assessments	Confirmed Response
sCR/CR/VGPR/PR/MR/SD	SD	SD
sCR/CR/VGPR/PR/MR	MR	MR
sCR/CR/VGPR/PR	PR	PR
sCR/CR/VGPR	VGPR	VGPR
sCR/CR	CR	CR
sCR	sCR	sCR

- B. For PD, since for this study, no confirmation of PD is required, only one PD assessment is required. Any PD assessment will be confirmed by itself at the time of the PD's assessment.
- C. If the subject has only one non-PD /non-NE assessment then the confirmed response is NE at the date of that assessment.
- D. If all assessments were NE then the confirmed response is NE at the date for each assessment.

Step 2. Determine the best overall confirmed response in Step 1. If assessments at all visits are missing then the best confirmed response is NE.

Examples:

Example 1.

Step1.

Visit	Response	Confirmed response
1	PR	
2	SD	SD
3	SD	SD

Step 2.

The best overall confirmed response is SD

Example 2.

Step1.

Visit	Response	Confirmed response
1	VGPR	
2	NE	
3	NE	
4	PR	PR

Step 2.

The best overall confirmed response is PR

Example 3.

Step1.

Visit	Response	Confirmed response
1	sCR	
2	sCR	sCR
3	CR	CR
4	PR	PR

Step 2.

The best overall confirmed response is sCR

Example 4.

Step1.

Visit	Response	Confirmed response
1	sCR	
2	CR	CR
3	CR	CR
4	PR	PR

Step 2.

The best overall confirmed response is CR

Example 5.

Step1.

Visit	Response	Confirmed response
1	CR	
2	VGPR	VGPR

Step 2.

The best overall confirmed response is VGPR.

7.2.1.2. Summary Measure

Overall response rate (ORR) and the associated 2-sided 95% exact confidence intervals will be provided by dose level and study part. In addition, Clinical Benefit Rate (CBR), defined as the percentage of subjects with minimal response (\geq MR) will be summarized in the same way as ORR by dose level and study part. Unconfirmed response summaries may be provided for interim analyses. A list of investigator-assessed response at each visit will be listed.

7.2.1.3. Population of Interest

The secondary efficacy analyses will be based on the “All Treated” population, unless otherwise specified. Response data for multiple myeloma will be summarized by Study Part using the All Treated MM population and in subgroup: Prior anti-cancer therapy of interest as defined in Section 5.2.1.

7.2.2. Lymphoma**7.2.2.1. Endpoint / Variables****7.2.2.1.1. Overall Response Rate**

For lymphoma patients, clinical activity for lymphomas will be calculated based on ORR defined as the percentage of subjects with confirmed CR or PR, as described in the Revised Response Criteria for Malignant Lymphoma (RRCML, Appendix 2 in the protocol) from the start of treatment until disease progression or the start of new anti-cancer therapy.

A summary of investigator-assessed best response with confirmation will be presented. Subjects with Not Evaluable or missing response will be treated as non-responders; and they will be included in the denominator when calculating the percentage. To be assigned a status of complete response or partial response, all responses must be confirmed by repeat assessments performed no less than four weeks after the criteria for CR or PR were met (RRCML, Appendix 2 in the protocol).

7.2.2.2. Summary Measure

Overall response rate and the associated 2-sided 95% exact confidence intervals will be provided. A list of investigator-assessed response at each visit will be listed.

7.2.2.3. Population of Interest

The secondary efficacy analyses will be based on the “All Treated” population, unless otherwise specified. Response data for lymphoma will be summarized using the Part 2 NHL population.

7.2.3. Strategy for Intercurrent (Post-Randomization) Events

Not applicable to this study.

7.2.4. Statistical Analyses / Methods

Details of the planned displays are provided in [Appendix 12: List of Data Displays](#) and will be based on GSK data standards and statistical principles.

Unless otherwise specified, endpoints / variables defined in Section [7.2.1](#) will be summarised using descriptive statistics, graphically presented (where appropriate) and listed.

7.3. Exploratory Efficacy Analyses

7.3.1. Multiple Myeloma

7.3.1.1. Endpoint / Variables

Time-to-event endpoint - Multiple Myeloma	
Progression-Free Survival (PFS)	defined as the time from first dose until the earliest date of confirmed disease progression (PD) per IMWG (2011), or death due to any cause.
Time to Progression (TTP)	defined as the time from first dose until the earliest date of PD per IMWG (2011), or death due to PD.
Duration of Response (DOR)	defined as the time from first documented evidence of confirmed PR or better until the time when disease progression (PD) is documented per IMWG (2011), or death due to PD among subjects who achieve a response (i.e. confirmed PR or better).
Time to Response (TTR)	defined as the time between the date of first dose and the first documented evidence of confirmed response (PR or better), among subjects who achieve a response (i.e., confirmed PR or better).
Time to Best Response (TTBR)	defined as the time between the date of first dose and the best confirmed response (PR or better), among subjects who achieve a response (i.e., confirmed PR or better).
Overall survival (OS)	defined as the time from the date of first dose until death from any cause.

In addition, monoclonal protein and serum free light chain lab test values will be plotted. Subgroup analysis for ORR will be performed

7.3.1.2. Summary Measure

7.3.1.2.1. Progression-Free Survival

PFS is defined as the interval of time between the date of first dose and the earlier of the date of first disease progression and the date of death due to any cause. Disease progression will be based on the assessments by the Investigator.

If there is no adequate baseline assessment, the subjects will be censored at their date of first dose. Subjects without any adequate post-baseline tumor assessments will be censored at the date of first dose.

Subjects who progressed or died after an extended period without adequate assessment will be censored at their date of last adequate assessment prior to progression or death even if subsequent information is available regarding progression or death. An adequate assessment is defined as an assessment where the Investigator determined response is sCR, CR, VGPR, PR, MR or SD. The date of response at that assessment will be used for censoring. As the assessment schedule may change through the course of the protocol, specific rules for identifying extended loss to follow-up or extended time without an adequate assessment are provided in Section 16.5.4.

For subjects who receive subsequent anti-cancer therapy the following rules will apply:

- If the start date of the anti-cancer therapy is partial (i.e. either missing the day but has the month and year available or missing both day and month), the imputation rules described in Section 16.7.2.1 will be applied. No imputation will be made for completely missing dates.
- If anti-cancer therapy is started without documented disease progression or death OR is started prior to documented disease progression or death, then PFS will be censored at the date of the last adequate assessment that is no later than the date of initiation of anti-cancer therapy (i.e. if an assessment occurs on the same day as the start of new anti-cancer therapy the assessment will be used - as it will be assumed the assessment occurred prior to the administration of new anti-cancer therapy). The date of response at the last adequate assessment will be used as the censoring value.
- If a subject has only a baseline visit or does not have an adequate assessment that is no later than the date of initiation of anti-cancer therapy, PFS will be censored at the date of first dose.
- If a subject has neither progressed nor died nor started new anti-cancer therapy, then PFS will be censored at the date of the last adequate assessment defined as an assessment where the Investigator determined response is sCR, CR, VGPR, PR, MR or SD. The date of response will be used as the censoring date.

A summary of the assignments for progression and censoring dates for PFS are specified in Table 5.

Table 5 Assignments for Progression and Censoring Dates for PFS Analysis

Situation	Date of Event (Progression/Death) or Censoring	Outcome Event (Progression/Death) Or Censored
No (or inadequate) baseline tumor assessments ^[1] and the subject has not died (if the subject has died follow the rules for death indicted at the bottom of the table)	First dose date	Censored
No post-baseline assessments and the subject has not died (if the subject has died follow the rules for death indicted at the bottom of the table)	First dose date	Censored
Progression documented between scheduled visits	Date of assessment of progression ^[1]	Event
No progression (or death)	Date of last 'adequate' assessment of response ^[2]	Censored
New anticancer treatment started (prior to documented disease progression or death) ^[3] .	Date of last 'adequate' assessment of response ^[2] (on or prior to starting anti-cancer therapy)	Censored
Death before first PD assessment (or Death at baseline or prior to any adequate assessments)	Date of death	Event
Death between adequate assessment visits	Date of death	Event
Death or progression after an extended loss-to-follow-up time (two or more missed cycles + 7 day window) ^[4]	Date of last 'adequate' assessment of response ^[2] (prior to missed assessments)	Censored

1. In part 1, adequate baseline assessment is defined as at baseline, a patient has at least one of the following measurements: a. Serum M-protein or b. Urine M-protein or c. Serum FLC assay or d. Biopsy proven plasmacytoma (should be measured within 28 days of Screening Visit).

In part 2, adequate baseline assessment is defined as at baseline, a patient has at least one of the following measurements: a. Serum M-protein ≥ 0.5 g/dL (≥ 5 g/L) or b. Urine M-protein ≥ 200 mg/24h or c. Serum FLC assay: Involved FLC level ≥ 5 mg/dL (≥ 50 mg/L) and an abnormal serum free light chain ratio (< 0.26 or > 1.65) or d. Biopsy proven plasmacytoma (should be measured within 28 days of Screening Visit and no later than the first dose date).

2. An adequate assessment is defined as an assessment where the Investigator determined response is sCR, CR, VGPR, PR, MR, or SD.

3. If PD or death and New anti-cancer therapy occur on the same day assume the progression or death was documented first (e.g., outcome is progression or death and the date is the date of the assessment of progression or death). If anti-cancer therapy is started prior to any adequate assessments, censoring date should be the date of first dose.

4. Refer to Section 16.5.4 "Extended Loss to Follow-up or Extended Time without an Adequate Assessment".

PFS will be summarized using Kaplan-Meier curves. If there are a sufficient number of progressions or deaths, median PFS, first and third quartiles and 95% CI, will be estimated using the Brookmeyer-Crowley method [Brookmeyer, 1982]. A figure and listing of PFS time will also be provided. Summary and figure of PFS will be based on

Part 2 MM sub-population and subgroup prior anti-cancer therapy of interest; listing of PFS will be based on All Treated MM population.

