16.5.4. Extended Loss to Follow-up or Extended Time without an Adequate Assessment

For subjects, if two or more scheduled disease assessments are missed and are then followed by an assessment of PD or death, PFS will be censored at the last adequate assessment prior to PD or death. When the scheduled disease assessment is every 3 weeks, a window of 49 days (6 weeks + 7 day window) will be used to determine whether there was an extended time without adequate assessment. That is, if the time difference between PD/death and last adequate assessment is more than 49 days, then PFS will be censored at the last adequate assessment prior to PD/death.

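### Read literally, the PFS text in section 7.3.1.2.1 censors at first dose subjects who progress at their first assessment or die before any adequate one, contrary to the PFS definition and Table 5

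*SAP*

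**What the plan says.** Section 7.3.1.2.1 defines PFS as running from first dose to "the earlier of the date of first disease progression and the date of death due to any cause". It then gives censoring rules in prose. One reads: "Subjects without any adequate post-baseline tumor assessments will be censored at the date of first dose". The same section fixes the key term: "An adequate assessment is defined as an assessment where the Investigator determined response is sCR, CR, VGPR, PR, MR or SD". PD and NE are therefore not adequate. The sentence on subjects without an adequate baseline assessment also censors at first dose, with no condition on survival.

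Table 5, introduced as a summary of these assignments, differs. Its row for missing post-baseline assessments applies only when there are none and the subject is alive. Its row for a missing or inadequate baseline likewise applies only to subjects still alive. The row "Death before first PD assessment (or Death at baseline or prior to any adequate assessments" is an event at the date of death. The progression row reads "Progression documented between scheduled visits", whereas the matching TTP row in Table 6 also names progression found at a scheduled visit.

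**The concern.** The prose rule turns on whether an adequate assessment exists, and adequacy is defined by non-progression. It therefore captures the subjects who fail fastest. Censoring them at time zero removes them from both the events and the risk set, so the censoring is informative and can only lengthen PFS.

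Two programmers, one working from the prose and one from Table 5, could produce different curves. The Part 2 MM PFS summary, its Kaplan-Meier figure and the subgroups by prior therapy all rest on this derivation. The exposure-response dataset in section 16.10.1 also takes over the PFS time and censoring flag, and uses the PFS time as the time to response for non-responders.

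**Working it through.** The SAP states no figure to reproduce here, so the main check sets the rules side by side.

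| Subject | Prose, 7.3.1.2.1 | PFS definition | Table 5 |
|---|---|---|---|
| (a) First post-baseline assessment is PD | Censored at first dose | Event at PD | Not in the first-dose censoring row, since an assessment exists; the progression row makes it an event but names only PD between visits |
| (b) Dies before any adequate assessment | Censored at first dose | Event at death | Event at death |
| (c) Inadequate baseline, then dies | Censored at first dose | Event at death | Sent to the death rows |
| (d) Alive, no post-baseline assessment | Censored at first dose | No event | Censored at first dose |

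Prose and table agree on (d). They conflict outright on (b) and (c). On (a) the prose conflicts with the definition, and Table 5 sides with the definition except for the gap in its progression row.

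**Size by Kaplan-Meier algebra.** Inputs: n = 40, the maximum for the Part 2 MM cohort (section 2.3), and k affected subjects, which is assumed. With no other early censoring, Table 5 gives S(t) = (1 − k/40) × R(t), where R(t) is the curve for the remaining subjects. The prose rule gives R(t) alone. The ratio is 1/(1 − k/40). Where Table 5 would give 0.50, the prose gives:

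- k = 2: 0.50/0.95 = 0.526
- k = 4: 0.50/0.90 = 0.556
- k = 8: 0.50/0.80 = 0.625

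**Size by simulation.** Assumptions: 40 subjects, exponential PFS, assessment every 3 weeks, follow-up uniform from 9 to 18 months, 1,500 runs per scenario. PD at the first assessment is recoded as censored at day 0. Early deaths are not modelled separately.

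| True median (months) | Mean number recoded | Median, Table 5 → prose | 6-month PFS, Table 5 → prose |
|---|---|---|---|
| 3 | 5.8 | 3.45 → 4.14 | 0.279 → 0.327 |
| 6 | 3.1 | 6.21 → 6.90 | 0.527 → 0.572 |
| 9 | 2.1 | 8.97 → 9.66 | 0.653 → 0.690 |
| 12 | 1.6 | 12.42 → 13.11 | 0.727 → 0.756 |

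The median moves by 0.69 months in each scenario, which is one 21-day assessment interval. Six-month PFS rises by about 3 to 5 percentage points.

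**The case against.** The best defence is that Table 5 is the row-by-row specification and already treats early deaths correctly, while the opening definition makes first progression an event. On that reading, bias arises only if a programmer follows one sentence in isolation. The second new-therapy bullet is confined to therapy begun without, or before, documented progression or death, and a Table 5 footnote keeps PD or death as the outcome even on the day new therapy starts. The planned PFS listing shows each subject's event or censoring description, so a misassignment would be visible. All of this stands, and it makes the bias conditional. It does not remove the contradiction, because no statement gives Table 5 precedence.

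Three stronger readings are tempting and not supported:

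- **Confirmed PD.** Section 7.3.1.1 defines PFS as "time from first dose until the earliest date of confirmed disease progression (PD", while section 7.2.1.1.2 says "since for this study, no confirmation of PD is required, only one PD assessment is required". A reader might infer a conflict. The latter section goes on to treat each PD as its own confirmation, so the word adds no requirement.
- **A greatly inflated median.** If 20% or 30% of subjects failed at the first assessment and 6-month PFS were still 50%, the prose rule would give medians of about 8.9 or 12.4 months. The 30% case needs the later hazard to fall to ln(0.7/0.5)/6 = 0.056 per month after 30% had failed in three weeks. Nothing in the SAP supports such a drop. A constant hazard with a 6-month median implies about 7.7% failing by three weeks.
- **The 49-day rule.** Section 16.5.4 begins from two or more missed assessments, then says "if the time difference between PD/death and last adequate assessment is more than 49 days, then PFS will be censored". A reader might infer that a dose delay of more than 28 days (21 + 28 = 49) followed by PD is censored although no assessment was missed. That holds only if assessments move with the delayed cycle, which this document does not settle. Table 5 also states the rule as two missed cycles plus 7 days.

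**Conclusion.** The point holds as a contradiction within the SAP. For early deaths, including deaths after an inadequate baseline, prose and Table 5 disagree explicitly. For first-assessment PD, the prose disagrees with the section's own definition, and Table 5's progression row is worded too narrowly to settle it.

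The direction of the effect is certain if the prose is followed: PFS is overstated. The amount depends on a count the SAP does not give. Under the assumptions above it is about 0.7 months on the median, with early deaths adding to it. It would be wrong to say that reported PFS is inflated, since the table may be what is programmed. PFS is exploratory, the cohort is single-arm with no hypothesis test planned, and the futility rule uses confirmed responses, so no decision rule is affected. What is at risk is the accuracy and reproducibility of the reported PFS estimates.

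**What to change.** In section 7.3.1.2.1:

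- State that censoring at first dose for lack of assessments applies only to subjects with no evaluable post-baseline assessment who have neither progressed nor died.
- Add Table 5's survival condition to the sentence on inadequate baseline.
- State in the third new-therapy bullet that PD documented on or before the start of new therapy is an event.

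In Table 5, widen the progression row to cover PD at as well as between scheduled visits, matching Table 6. No change is needed to the word *confirmed* in section 7.3.1.1. In section 16.5.4, at most reconcile the missed-assessment condition with the 49-day count for subjects whose cycles are delayed.

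The cost is a few sentences and a check of the PFS derivation, with no new data. If the prose has already been programmed, reported PFS may become slightly shorter.

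### Read as written, the PFS text censors early deaths and first-result PD at first dose, against Table 5 and the PFS definition, and biases exploratory PFS upward

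*SAP*

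**What the plan says.** SAP Section 7.3.1.2.1 ends PFS at "the earlier of the date of first disease progression and the date of death due to any cause". The next paragraph sets the first-dose rule: "Subjects without any adequate post-baseline tumor assessments will be censored at the date of first dose". The paragraph after that gives the definition: "An adequate assessment is defined as an assessment where the Investigator determined response is sCR, CR, VGPR, PR, MR or SD". Table 5 footnote 2 repeats the same list. PD is in neither.

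Table 5, introduced as a summary of the assignments, is narrower. Its post-baseline row for first-dose censoring reads "No post-baseline assessments and the subject has not died" and sends deaths to the death rows. One of those rows, "Death before first PD assessment (or Death at baseline or prior to any adequate assessments", is an event on the date of death. Its only progression row is "Progression documented between scheduled visits", also an event. The matching row of Table 6 (TTP, Section 7.3.1.2.2) covers PD found at a visit as well as between visits.

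On subsequent therapy, the second bullet limits censoring to therapy started without, or before, documented PD or death. The third bullet has no such limit: if a subject "does not have an adequate assessment that is no later than the date of initiation of anti-cancer therapy, PFS will be censored" at first dose. The last sentence of Table 5 footnote 3 likewise sets first dose as the censoring date when therapy starts before any adequate assessment.

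**The concern.** Subjects who progress at the first assessment or die early have the worst outcomes in the cohort. Censoring them at time zero removes them from the risk set before any event, so the curve describes only subjects who were at least stable once. The error can go only one way, towards longer PFS.

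The SAP does not say whether the text or Table 5 governs, so two programmers could derive different PFS from the same data. It could also break the ordering of endpoints: PD at Cycle 2 Day 1 is a TTP event under Table 6, but under the PFS text the same subject is censored at first dose. The result would carry into the exposure-response dataset (Section 16.10.1), which takes PFS time and its censoring flag and uses PFS time as the time to response for non-responders.

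**Working it through.** **Comparing the rules.** The inputs are the text, Table 5 and its footnotes in Section 7.3.1.2.1, and Section 7.2.1.1.2, which accepts a single PD without confirmation, so PD at the first visit is a complete event.

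| Subject | PFS definition | Text, read literally | Table 5 |
|---|---|---|---|
| Alive, no post-baseline assessment | no event | first dose, censored | first dose, censored |
| Dies before any sCR-to-SD result | event | first dose, censored | event at death |
| No adequate baseline, then dies | event | first dose, censored | event at death |
| First result is PD, at a scheduled visit | event | first dose, censored | no row that literally fits; the first-dose row does not apply because an assessment exists |
| First result is PD, then new therapy | event | first dose, censored (also by the third bullet) | new-therapy row does not apply, but the last sentence of footnote 3 literally gives first dose |

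The deaths are a direct conflict between text and table. The PD rows conflict with the PFS definition, and Table 5 does not settle them explicitly. The gap concerns ordinary cases: Section 16.2.3.1 schedules the myeloma markers at Cycle 2 Day 1 and at the start of every later cycle, so a first PD will usually be found at a scheduled visit.

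**Size of the bias.** The SAP states no PFS figure to reproduce. Suppose x of n subjects have PD or death as the first events on the curve, with no other censoring before then. Counted as events, they contribute the factor (1 - x/n). Censored on Day 1, they contribute nothing, and every later risk set is unchanged. Hence

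S_text(t) = S_Table5(t) / (1 - x/n).

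Here S_Table5 counts both early deaths and first-result PD as events. The reported median then falls where that curve reaches 0.5 × (1 - x/n). Section 2.3 plans up to 40 MM subjects in Part 2, so with n = 40:

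| x | S_Table5 = 0.50 becomes | Estimate after the first visit, events counted / text | Reported median falls where S_Table5 is |
|---|---|---|---|
| 2 | 0.50/0.95 = 0.526 | 0.95 / 1.00 | 0.475 |
| 4 | 0.50/0.90 = 0.556 | 0.90 / 1.00 | 0.450 |
| 8 | 0.50/0.80 = 0.625 | 0.80 / 1.00 | 0.400 |
| 12 | 0.50/0.70 = 0.714 | 0.70 / 1.00 | 0.350 |

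**In months, under assumptions only.** The documents give no PFS median and no rate of first-visit PD.

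- *Single exponential.* Setting: n = 40, visits every 21 days, no other censoring, 3,000 simulated cohorts. For assumed medians of 3, 6 and 12 months, the text censors on average 5.9, 3.1 and 1.6 subjects on Day 1. The mean Kaplan-Meier median moves from 3.3 to 4.1, 6.2 to 7.0 and 12.2 to 13.1 months, about 0.7 to 0.9 months upward.
- *Separate refractory group.* Assume a share p has PD at the first visit and the rest are exponential with a 6-month median. With PD counted, the median is 6·log2(2(1 - p)), rounded up to the next 21-day visit. This gives 5.5, 4.1 and 3.4 months for p = 10%, 20% and 30%. If only that group is censored on Day 1, the median is 6.2 months each time.

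**The case against.** The strongest reply is that censoring rules ordinarily apply to subjects without an event. The section first defines PFS as ending at PD or death. Where it means censoring to override an observed event, as in the extended-gap rule, it says so, and the disputed sentence does not. Table 5 settles early death. For PD followed by therapy, the second bullet, the new-therapy row and the same-day rule in footnote 3 all treat documented PD as the event. If the Table 5 progression row truly excluded scheduled visits, it would miss nearly every progression, so the Table 6 wording suggests that words were dropped.

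Much of this stands as evidence of intent. A reader might infer that the plan means to discard primary progressors; those same provisions do not support that. It does not remove the defect, because the operative sentence is unqualified, the definition of adequate excludes PD, and no order of precedence is given.

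A reader might also infer damage to landmark PFS or a known bias of two months or more. Neither is supported. Section 7.3.1.2.1 plans Kaplan-Meier curves, the median and quartiles; the landmark analysis, at 9 and 12 months, is for OS (Section 7.3.1.2.6). The larger shifts arise only if a separate refractory group is assumed.

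**Conclusion.** The concern holds as a drafting contradiction with a one-directional effect. It is explicit for deaths before any adequate assessment. For PD as the first result it follows from the literal text, although the surrounding provisions show that PD was meant to count. The effect is an upward bias in the PFS curve, median and quartiles by a factor of about 1/(1 - x/n). That factor is exact only if nobody else is censored before these events. No firm figure in months can be given from the documents.

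This is a should-fix. PFS is exploratory (Section 2.2), no hypothesis test is planned for the Part 2 MM cohort (Section 2.4), and the PFS tables carry no hazard ratio or log-rank p-value (Section 16.12.6). The by-subject PFS listing (Section 16.12.13) would also expose a wrong assignment to anyone who checked it.

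**What to change.** Make four edits:

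1. Replace the sentence with: *Subjects with no post-baseline assessment of sCR to PD who have not died are censored at first dose; PD as the first result, or death before any adequate assessment, is an event on its date, subject to the extended-gap rule of Section 16.5.4.* State also how the 49-day window in that section applies when there is no adequate post-baseline assessment to count from, for example by counting from first dose. Otherwise a late first PD or death meets two competing rules.
2. Add to the no-adequate-baseline sentence the exception for deaths that Table 5 already makes.
3. Limit the third new-therapy bullet and the last sentence of footnote 3 to therapy started before documented PD or death.
4. Extend the Table 5 progression row to PD found at a scheduled visit, matching Table 6.

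The cost is SAP wording and a check of the PFS derivation. No new data are needed.
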